4.1.2. Tisagenlecleucel Product

Tisagenlecleucel is an autologous cellular immunotherapy product that is comprised of CD3+ T cells that have undergone *ex vivo* T cell activation, gene modification, expansion and formulation in infusible cryomedia. The transgene to be expressed via lentiviral vector transduction is a CAR targeted against the CD19 antigen. The CAR contains a murine scFv that targets CD19 linked to a transmembrane region derived from the CD8 receptor, which is linked to an intracellular bipartite signaling chain of TCR- ζ (or CD3- ζ) and 4-1BB intracellular signaling domains. The extracellular scFv with specificity for CD19 is derived from a mouse monoclonal antibody. T cells which were enriched from a patient leukapheresis unit are expanded *ex vivo* using commercially available magnetic beads that are coated with anti-CD3 and anti-CD28 monoclonal antibodies. The cells are transduced with the CD19 CAR lentiviral vector which ensures that only peripheral white blood cells enriched for lymphocytes are exposed to the vector. The residual non-integrated vector is washed away during the process. CTL019 cells will be expanded *ex vivo* for up to 10 days. At the end of the culture, the CTL019 cells are depleted of magnetic beads, washed, concentrated, and cryopreserved. Results from a release testing procedure are required prior to release of the product for infusion.

4.1.3. Tisagenlecleucel Dose:

A dose of Tisagenlecleucel transduced cells for patients will consist of a single infusion of 1 to 5 $\times 10^8$ Tisagenlecleucel transduced cells.

4.1.4 Tisagenlecleucel Infusion:

The Tisagenlecleucel cell product will be prepared and released by the manufacturing facility to the study site approximately 3 to 4 weeks after manufacturing has commenced, provided all required safety and quality release criteria have been met. Upon receipt of the cryopreserved CTL019 cell product, an inventory must be performed, and a drug receipt log filled out and signed by the person accepting the shipment. The cryopreserved tisagenlecleucel should be kept in the vapor phase of liquid nitrogen until infusion.

Prior to CTL019 infusion the following criteria must be met:

1. All patients must undergo a rapid influenza diagnostic test within 10 days prior to the planned CTL019 infusion. If the patient is positive for influenza, oseltamivir phosphate or zanamivir should be administered for 10 days as preventative treatment. The patient must complete their 10-day preventative treatment course **prior** to receiving tisagenlecleucel. The test does not need to be repeated prior to infusion however, if flu-like or respiratory signs and symptoms are present, CTL019 infusion should be delayed until the patient is asymptomatic.
2. COVID-19 screening will occur prior to duvelisib initiation [see section 5.6]. Based on medical assessment, CTL019 infusion will be delayed in symptomatic patients (symptoms including but not limited to fever, cough, sore throat, loss of taste/smell, headaches, myalgias) suspected to have active COVID-19 disease until the patient is asymptomatic.
3. Patient should not experience a significant change in clinical status compared to initial eligibility criteria that would, in the opinion of the treating physician, increase the risk of adverse events associated with experimental cell infusion.

4. Rapidly progressing patients, or patients experiencing laboratory abnormalities after enrollment, that in the opinion of the treating investigator or PI may impact patient safety or the patients' ability to receive the infusion, may have their infusion delayed until both the treating investigator and PI determine it is clinically appropriate to proceed with the infusion.
5. Patients experiencing toxicities from their preceding lymphodepleting chemotherapy will have their infusion schedule delayed until these toxicities have resolved. The specific toxicities wanting delay of infusion include:
 - a. Pulmonary: Requirement for supplements oxygen to keep saturation greater than 91% **or** presence of progressive radiographic abnormalities on chest x-ray
 - b. Cardiac: New cardiac arrhythmia not controlled with medical management
 - c. Hypotension requiring vasopressor support
 - d. Uncontrolled active infection, as evidenced by positive blood cultures for bacteria, fungus, or PCR positivity for viral DNA in blood within 72 hours of infusion, or clinical or radiographic evidence of active infection.

Following lymphodepleting chemotherapy patients must not have progressive disease in order to receive infusion, as this will potentially put them **at** an unacceptable risk for severe CRS. Patients should not receive infusion if they exhibit significant progression of disease following lymphodepleting chemotherapy as evidenced by:

- a. Significant increase in nodal disease
 - b. Significant increase in extra-nodal disease
 - c. Occurrence of new lymphoma manifestations
 - d. Clinical evidence of CNS disease
6. If patients are taking any of the following medications, their infusion must be delayed until the medications have been stopped according to the below:
 - a. Steroids: Therapeutic doses of steroids must be stopped >72 hours prior to tisagenlecleucel infusion. However, the following physiological replacement doses of steroids we allowed: 6-12 mg/m²/day hydrocortisone or equivalent
 - b. Antiproliferative Therapy:
 - c. All anti-proliferative therapies must have been stopped > 2 weeks prior to tisagenlecleucel infusion
 - d. Immunosuppressive therapies: Any drug used for immunosuppression must be stopped > 4 weeks prior to tisagenlecleucel infusion (e.g. calcineurin inhibitors, methotrexate or other chemotherapy drugs, mycophenolate, steroids [see above], rapamycin, thalidomide or immunosuppressive antibodies such as rituximab, anti-TNF, anti-IL6 or anti-IL6R)
 - e. CNS disease prophylaxis must be stopped 1 week prior to tisagenlecleucel infusion (e.g. intrathecal methotrexate).

Patients experiencing toxicities from their preceding chemotherapy will have their tisagenlecleucel infusion delayed until the above toxicities have been resolved. If any of the above criteria are not met and a period of delay is 4 or more weeks from completing lymphodepleting chemotherapy and the WBC is >1000/microL, the patient will need to be re-treated with lymphodepleting chemotherapy, and these criteria will need to be re-established prior to tisagenlecleucel infusion.

4.2 Drug/Device Handling

4.2.1 Acquisition and Accountability

Duvelisib will be provided by Secura Bio and will be packaged and labeled by Secura Bio.

Protocol Title: Duvelisib Exposure to Enhance Immune Profiles of T Cells in Patients with Diffuse Large B Cell Lymphoma (DEEP T CELLS)

The sponsor will acknowledge receiving the medication by completing and documenting forms indicating shipment content and condition. Records of duvelisib received at, dispensed from and returned by the study site will be documented in the drug inventory log (DIL). Duvelisib will be dispensed by clinical research staff per the protocol of the Winship Cancer Institute and dispensation of the study drug must be documented. Duvelisib should be taken at approximately the same times on each day and should be taken with 8 oz of water. Patients will be required to maintain a medication diary of each dose of medication. The medication diary (Appendix E) will be returned to clinic staff at the end of completion treatment or at the time of withdrawal from the study.

If a dose of duvelisib is missed by fewer than 6 hours, the missed dose can be taken right away and the next dose taken on schedule. If a dose is missed by more than 6 hours, the dose is skipped the next dose taken at the usual time. Patients will not be allowed to make up missed doses and a missed dose should also be recorded in the patient's diary. Incorrect dosing should also be reported in the patient's diary and documented in the case report form. Damaged medication will be replaced.

Patients will be asked to return all unused duvelisib and packaging at the end of the study or at the time of study treatment discontinuation. Duvelisib supply will be disposed of per Winship's Investigational Drug Service (IDS) SOP. Compliance will be assessed by the investigator and/or study personnel at each patient visit and information provided by the patient and/or caregiver (collection of drug diary) will be captured in the Drug Accountability Form. This information must be captured in the source document at each patient visit. Dose changes and interruptions of study drug must be specifically documented in the patient source documents and eCRF.

4.2.2. Formulation, Appearance, Packaging and Labeling

Duvelisib comes in two strengths: 15mg and 25mg. Patients will be provided twenty-eight (28) 25mg tablets. The contents of the label will be in accordance with regulatory requirements.

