5.1 Study Design

This is an open-label pilot clinical trial prospective study of treating patients with relapsed/refractory DLBCL or relapsed/refractory follicular lymphoma with duvelisib at a dose of 25 mg p.o. b.i.d. for 8 to 15 days prior to collection of mononuclear cells by apheresis for the purpose of CAR-T manufacturing. The intended duration of duvelisib exposure is 2 weeks. The duration of duvelisib may be adjusted to a period between 8 and 15 days depending upon the schedule of apheresis, with the last dose of duvelisib on the day of apheresis.

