5.7 Description of Study Procedures

Definition of Study Assessments

All patients will be closely monitored for safety and tolerability throughout the study. Patients will continue dosing until they experience intolerable AE's, patient withdrawal or termination of the study. Patients may be discontinued from study treatment in the following situations: 1) patients has decided to withdrawal from the study, 2) Intolerable adverse events, 3) confirmed disease progression or lack of benefit, 4) pregnancy, or 5) severe noncompliance (including but not limited to receiving less than 75% of duvelisib doses (23/28 doses). The schedule of activities is listed in section 1.3.

Medical History

Medical history and demographics will be collected at screening. Medical history will include other significant co-morbidities, previous surgeries, cancer history, previous chemotherapy and outcomes, use of tobacco, alcohol and recreational drugs and any known toxin exposure. Demographics data will include age, sex and self-identified race/ethnicity.

Performance Status

The ECOG performance status (see appendix A) will be assessed at screening and throughout the study (days 1, 8 and 15 during treatment with duvelisib; days 7,14,28,42 and 90 post CAR-T infusion).

Physical Exam

Physical exam will include examination of all body systems, including assessment of general appearance, weight, height, head, neck, lymph nodes, heart, lungs, abdomen, extremities, skin and nervous system. A physical exam will be performed on screening and on days 1,8 and 15.

Laboratory Data

Blood samples for chemistry, hematology, viral serologies, leukocyte immunophenotyping and pregnancy (for pre-menopausal patients) will be analyzed at Winship Cancer Institute laboratory. The chemistry panel will include sodium, potassium, chloride, bicarbonate, glucose, BUN, AST, ALT, total bilirubin, total protein, thyroid stimulating hormone and magnesium will be tested at screening and on days, 1,8 and 15. Hematology panel includes complete blood count, including white blood cell count with differential (neutrophils, lymphocytes, eosinophils, basophils), red blood cell count, hemoglobin, hematocrit and platelet count will be tested at screening and days 1, 8 and 15. Viral serologies will be tested at screening and include:

- HIV antigen/antibody
- Hepatitis B Panel (HBsAg, HBsAb, HBcAb and HBV DNA PCR if HBcAb is positive)
- Hepatitis C Panel (HCV Ab and HCV PCR if HCV Ab is positive)

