17.5.1 Study Design Endpoints

This is pilot study to examine if exposure to a dual PI3K delta and gamma inhibitor before CAR T cell leukapheresis leads to decreases in manufacturing time and enhanced expression of CD27/CD28+ T cells. Patients who receive at least 75% (23/28 doses) of duvelisib will be evaluable for final analysis. Patients who do not receive 75% of doses will be considered unevaluable and replaced. Patients who do not undergo leukapheresis within two (2) days of completion of the 8 to 15 days of duvelisib will be considered unevaluable and replaced. All patients with any exposure to duvelisib will be evaluable for toxicity (please see section 13.3 on grading of toxicities).

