17.5.2 Analysis of Primary Endpoints

All patients that complete >75% of planned duvelisib doses and undergo leukapheresis within 2 weeks of duvelisib treatment completion will be included in the final analysis of the primary endpoint. The primary endpoint of the study to estimate the fold-change increase in CD27/CD28 double positive T cells following *in vivo* exposure to duvelisib from baseline to day 15. Our in vitro studies have shown that culturing DLBCL patients' T cells with 14 days of duvelisib increased the amount of CD27/CD28 double positive T cells from 12.2% to 32.7% (Petersen, et al, supplemental data). However, there are currently no *in vivo* background data to benchmark the expected fold-change CD27/CD28 double positive T cells over a 14-day window. Therefore, with 20 patients, this pilot study will be based on estimation on the fold change increase only and will not include a formal evaluation of the change against a null unpromising fold-change. However, we will consider this study promising if there is at least a two-fold increase in CD27+/CD28+ in at least 75% of patients.

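### The fixed 28 no longer fits 8- to 15-day courses: 28 tablets fall 1 to 2 short of a 15-day course begun with a morning dose, and fully adherent patients on 8 to 11 days cannot reach the 23/28 dose threshold

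*Combined protocol and SAP*

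**What the plan says.** **Regimen.** Section 5.1 prescribes "duvelisib at a dose of 25 mg p.o. b.i.d. for 8 to 15 days prior to collection of mononuclear cells by apheresis". Two weeks is the intended length, but "The duration of duvelisib may be adjusted to a period between 8 and 15 days depending upon the schedule of apheresis". The same section also fixes when dosing ends: "with the last dose of duvelisib on the day of apheresis".

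**Supply.** Section 4.2.2: "Patients will be provided twenty-eight (28) 25mg tablets". The only further supply mentioned is in section 4.2.1: "Damaged medication will be replaced". Unused tablets are returned under the same section.

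**Threshold.** Section 17.5.1: "Patients who receive at least 75% (23/28 doses) of duvelisib will be evaluable for final analysis". Patients below the threshold are to be replaced. Section 5.7 gives, as an example of severe noncompliance and a ground for stopping study treatment, "receiving less than 75% of duvelisib doses (23/28 doses". Section 17.5.2 defines the primary analysis set without a fixed denominator: "All patients that complete >75% of planned duvelisib doses". Section 17.5.3 uses the 75% level again, without a count, for the compliance endpoint (item 1) and for the patients in the manufacturing-time summary (item 2).

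**The concern.** The number 28 belongs to a 14-day course. Once the course may run from 8 to 15 days, a fixed 28 is too small as a supply at the upper end and too large as a denominator at the lower end.

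On supply, a patient who takes the first tablet in the morning of Day 1 and has apheresis on Day 15 takes the 28th tablet on the evening of Day 14. None is left for the apheresis day, when section 5.1 wants the last dose taken.

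On the threshold, a course shortened to suit the apheresis slot is permitted, but a patient who takes every dose of it may still fall below 23. Section 17.5.1 would then remove and replace that patient, while section 17.5.2 would keep the same patient in the primary analysis. In a study of 20 patients, judged promising if at least 75% of them show a two-fold increase, membership of the denominator matters. Two analysts could build different analysis sets from the present text.

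**Working it through.** **Inputs.** 25 mg twice daily, so one 25 mg tablet per dose and two per day (5.1, 4.2.2); 28 tablets supplied (4.2.2); courses of D = 8 to 15 days (5.1); threshold of 75%, written as 23/28 (5.7, 17.5.1). The documents do not say whether the first and last days carry one dose or two, so all cases are shown.

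**Reproducing the plan's figure.** 2 x 14 = 28 tablets, which matches the intended two weeks.

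**Doses in a course of D calendar days.**
- Morning first, evening last: 2D
- Morning first and last, or evening first and last: 2D - 1
- Evening first, morning last: 2D - 2

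| Days | 2D | 2D-1 | 2D-2 | Tablets short of 28 (same order) | 23 / 2D | 2D / 28 | 75% of 2D, rounded up |
|---|---|---|---|---|---|---|---|
| 8 | 16 | 15 | 14 | 0 / 0 / 0 | 144% | 57% | 12 |
| 9 | 18 | 17 | 16 | 0 / 0 / 0 | 128% | 64% | 14 |
| 10 | 20 | 19 | 18 | 0 / 0 / 0 | 115% | 71% | 15 |
| 11 | 22 | 21 | 20 | 0 / 0 / 0 | 105% | 79% | 17 |
| 12 | 24 | 23 | 22 | 0 / 0 / 0 | 96% | 86% | 18 |
| 13 | 26 | 25 | 24 | 0 / 0 / 0 | 88% | 93% | 20 |
| 14 | 28 | 27 | 26 | 0 / 0 / 0 | 82% | 100% | 21 |
| 15 | 30 | 29 | 28 | 2 / 1 / 0 | 77% | 107% | 23 |

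**Supply.** Only D = 15 can exceed 28. A morning start leaves the patient 30 - 28 = 2 or 29 - 28 = 1 tablet short. With an evening start and an evening finish the shortfall is 1, but the apheresis-day morning dose is still covered. With an evening start and a morning finish 28 is exactly enough. The effect on the threshold is nil: 28/30 = 93.3%, well above 75%.

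**Threshold read as a count of 23.** At 8 to 11 days the most doses possible are 16 to 22, so 23 is out of reach. This is the boundary under the most generous count. At 12 days with an evening start and a morning finish, full adherence gives 22, also below 23.

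**Threshold read as 75% of a fixed 28 (21 doses).** Full adherence over 8, 9 or 10 days gives 16/28 = 57%, 18/28 = 64% and 20/28 = 71%, all below 75%. Dropping the 23 but keeping the 28 therefore does not repair the rule.

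**Threshold as printed for 14 days.** 23/28 = 82.1%, whereas 0.75 x 28 = 21. The percentage and the count disagree even for the intended course. (0.75 x 30 = 22.5, so 23 is the 75% count for a full 15-day course.)

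**The case against.** **On supply.** The intended course is two weeks, and 28 tablets match it. The gap exists only at 15 days and not in every dosing pattern. Apheresis on Day 15 after a last tablet on the evening of Day 14 is still inside the two-day window in sections 7.1 and 17.5.1. Section 4.2.2 states a quantity, not a maximum; section 4.2.1 leaves dispensing to site procedures that the reader cannot see; and missed doses are not made up, so any missed dose leaves a spare tablet. All of this stands. It makes the supply point an operational correction: the text conflicts with the last-dose wording in 5.1, but no patient is lost.

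**On the threshold.** The rule is stated as a percentage wherever it appears, and the sentence after the one quoted from 17.5.1 repeats 75% without a count. A sensible statistician could take 23/28 as an illustration for the 14-day course and use planned doses. That reading limits the likely damage but does not rescue the text. Nothing marks 23/28 as an example, and as an example it is wrong, since 75% of 28 is 21. Section 17.5.1 also refers to 8 to 15 days in the same paragraph as the fixed count, so the rule and the variable course stand side by side unreconciled.

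**Conclusion.** The concern holds on both parts, and its severity is minor.

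The supply in 4.2.2 is 1 to 2 tablets short for a 15-day course begun with a morning dose, and adequate for 8 to 14 days. The threshold matters more. If 23 is applied as a count, every fully adherent patient on 8 to 11 days is unevaluable under 17.5.1 although 17.5.2 would include them, and the same patients meet the noncompliance example in 5.7.

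This rests on one tablet per dose, two doses per day and the first and last doses falling as shown. How many of the 20 patients would be affected cannot be calculated, because the plan gives no expected distribution of course lengths. A probable cause is that the change log entry for the move from two weeks to 8 to 15 days lists sections 1.1, 2, 3.2 and 5.1 but not 4.2.2, 5.7 or 17.5. The conclusion rests on the current text, not on that log.

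**What to change.** - **4.2.2:** supply at least 30 tablets per patient. This covers every permitted course, and returns are already handled under 4.2.1.
- **5.7 and 17.5.1:** delete the 23/28 count and define the threshold as at least 75% of the patient's own planned doses, meaning the doses scheduled from first dose to apheresis. For full twice-daily courses that is 12 of 16 at 8 days, 21 of 28 at 14 days and 23 of 30 at 15 days.
- **17.5.2:** its planned-dose denominator can stay. Its strict inequality should be aligned with the at-least wording of 17.5.1, since exactly 75% can occur (12 of 16, 21 of 28).

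The cost is one number, a phrase in each of the threshold sections and a pharmacy instruction. Design, sample size and visits do not change.

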4.2.3 Product Storage and Stability

Duvelisib will be stored at the Emory Investigational Pharmacy. Duvelisib will be stored at room temperature between 20-25 degrees Celsius.

4.2.4. Safety of Duvelisib

Immune related toxicities are the most common non-hematological adverse event (AE) with duvelisib. Infection, elevated AST/ALT and diarrhea are the most common non-hematological AEs. The rates of diarrhea ranged from 42-51% in clinical trials with a median onset of 2.2-4 months.^{35,36} The median time of onset for AST/ALT elevation was 1.2 months and occurred in 39% of patients in one phase I clinical trial.³⁵ Other non-hematological AE's that have been reported include maculopapular rash, pyrexia and colitis. Neutropenia was the most common hematological AE, occurring in 29%-39% of patients in clinical trials. Infections has also been reported in 61-69% of patients with upper respiratory tract infections and pneumonia being the most common infections.^{36,37} There have also been reports of Pneumocystis jiroveci with the use of duvelisib.

5. Procedures Involved

5.1 Study Design

This is an open-label pilot clinical trial prospective study of treating patients with relapsed/refractory DLBCL or relapsed/refractory follicular lymphoma with duvelisib at a dose of 25 mg p.o. b.i.d. for 8 to 15 days prior to collection of mononuclear cells by apheresis for the purpose of CAR-T manufacturing. The intended duration of duvelisib exposure is 2 weeks. The duration of duvelisib may be adjusted to a period between 8 and 15 days depending upon the schedule of apheresis, with the last dose of duvelisib on the day of apheresis.

5.2 Dosing and Administration

In the phase I study with duvelisib in hematological malignancies, the maximum tolerated dose (MTD) was 75mg BID. However, peak inhibition of the p-AKT pathway was not dose dependent and was maximally inhibited at 25mg BID, and this is the FDA approved dose.³⁵

5.3 Interruption/Disruption of Treatment

Duvelisib is a BID medication. Doses that are missed or not absorbed (i.e., vomiting) will not be made up with additional dosing after the 8 to 15 day study period.

Duvelisib can be stopped for any clinically significant toxicity, including if any of the following are observed:

- Grade 3 or 4 hematologic toxicity (19) as defined by the CTCAE version 5.0)
- Grade 3 or 4 non-hematological toxicity

For grades 1-2 as defined by the CTCAE, will not have any dose modifications and will be treated with supportive care. If study drug is stopped due to an AE, it will not be resumed, and the patient may proceed to leukapheresis on schedule. No allowance will be made for dose interruptions

